18.C.8 Informed Consent	44
18.C.9 Institutional Review Board or Ethical Review Committee (IRB or ERC)	44
18.C.10 Protocol Amendments and Emergency Deviations	45
18.C.11 Monitoring of Study sites by the Sponsor's Representative	45
18.C.12 Case Report Forms and Study Records.....	46
18.C.13 Laboratory Certification and Normal Ranges	46
18.C.14 Drug Accountability	46

18.C.15	Record Retention	46
18.C.16	Inspection of Records	46
ATTACHMENT D: PACKAGE INSERTS.....		47
ATTACHMENT E: PROTOCOL SIGNATURE PAGE		48

LIST OF ABBREVIATIONS

AE	Adverse Event
CD4	Cluster of differentiation antigen 4
CDC	Centers for Disease Control and Prevention
CFR	Code of Federal Regulations
CRF	Case Report Form
CV	Curriculum Vitae
DCC	Data Coordination Center
DNA PCR	Deoxyribonucleic acid polymerase chain reaction
EC	Ethics Committee
EIA	Enzyme Immunoassay
ELISA	Enzyme-linked Immunosorbent Assay
ERC	Ethical Review Committee
FDA	Food and Drug Administration
GCP	Good Clinical Practice
HAART	Highly Active Antiretroviral Therapy
HIV	Human Immunodeficiency Virus
HJF	Henry M. Jackson Foundation
HSRRB	Human Subjects Research Review Board
HURC	Human Use Review Committee
ICH	International Conference on Harmonization
IDCRP	Infectious Disease Clinical Research Program
IRB	Institutional Review Board
MRSA	Methicillin-resistant Staphylococcus aureus
MSM	men who have sex with men
MSSA	Methicillin-sensitive Staphylococcus aureus
NIAID	National Institute of Allergy and Infectious Diseases
NIH	National Institutes of Health
NMCP	Naval Medical Center Portsmouth
NMCSD	Naval Medical Center San Diego
NOS	Not otherwise specified
OHRP	Office of Human Research Protections
OTSG	Office of the Surgeon General
PI	Principal Investigator
PIN	Participant Identification Number
PVL	Panton-Valentine Leukocidin
RCHSPB	Regulatory Compliance and Human Subjects Protection Branch
RNA-PCR	Ribonucleic acid polymerase chain reaction
SAE	Serious Adverse Event
SAMHS	San Antonio Military Health System
SAMMC	San Antonio Military Medical Center
SOP	Standard Operating Procedure

SPI	Site Principal Investigator
TMP/SMX	Trimethoprim-sulfamethoxazole
USMHRP	U.S. Military HIV Research Program
USUHS	Uniformed Services University of the Health Sciences
WHASC	Wilford Hall Ambulatory Surgical Center
WRNMMC	Walter Reed National Military Medical Center at Bethesda

I. PRECIS

Methicillin-resistant *Staphylococcus aureus* (MRSA) infections have dramatically increased over the past decade with novel community-acquired isolates occurring worldwide [1, 2]. Despite that many of these community-acquired MRSA infections are skin or soft tissue infections occurring in young, otherwise healthy individuals, they have been associated with high hospitalization rates and the potential for severe complications [1, 3-5]. The most common risk factors for community-acquired MRSA infections among the general population have been prior antibiotic use, prior hospitalization, injection drug use, and contact with a person with MRSA-infection [6-10].

Human immunodeficiency virus (HIV) infection is also a known risk factor for both MRSA colonization and infection [7, 8, 11]. To date, only retrospective studies have examined the incidence rates and the predictors for community-acquired MRSA among HIV-infected persons [7, 12, 13]. Furthermore, whether HIV patients should be screened routinely for MRSA carriage and whether decolonization procedures, with hexachlorophene (also known as pHisoHex® soaps) soaps and nasal mupirocin, should be instituted remains unknown as there are no formal guidelines or prospective studies addressing these questions.

This study will prospectively evaluate the prevalence and incidence (over a two year period) of MRSA colonization and infection among HIV-infected military beneficiaries to determine predictors for the development of MRSA colonization and infection. This study will also investigate the utility of decolonization procedures for clearance of MRSA carriage and prevention of MRSA infections. The molecular characteristics and the antimicrobial sensitivities of isolates in this population will be determined.

Additionally, medical records of HIV-infected patients seen at the HIV clinic at NMCSD will be evaluated to determine the incidence and clinical features of MRSA infections among this population. This is an ongoing evaluation (IDCRP-049) since 2006 (date of study initiation) that utilizes previously collected information (since 1993 until March 1, 2011) found within the patients' medical records, and does not require contact with the patients and does not collect any new information. The purpose of this study is to determine the incidence of MRSA among a total HIV population. This ongoing chart review is merged into this prospective study as both studies aim to evaluate the impact of MRSA infections in HIV-infected persons.

II. STUDY SITES

Sponsor	Infectious Disease Clinical Research Program (IDCRP) Uniformed Services University of the Health Sciences (USUHS) [name] National Institutes of Health (NIH) National Institute of Allergy and Infectious Disease (NIAID) [name] [name] 20892-5138
Monitoring Team	Regulatory Compliance and Human Subjects Protection Branch (RCHSPB) [name]
Laboratory	San Antonio Military Medical Center [name] [contact]

Naval Medical Center San Diego (NMCSD) Infectious Disease Division [name] [contact] [contact]
Walter Reed National Military Medical Center (WRNMMC) Infectious Disease Clinic [name] [name] 20889 [contact] [contact]
Wilford Hall Ambulatory Surgical Center (WHASC) Infectious Disease Department [name] [contact] [contact]
San Antonio Military Medical Center (SAMMC) [name] [contact]
Naval Medical Center Portsmouth (NMCP) [name] [contact]

III. OBJECTIVES

3.1 Primary Objectives

To evaluate the effectiveness of decolonization procedures with application of hexachlorophene (pHisoHex®) soaps and nasal mupirocin (Bactroban®) compared to a placebo soap and nasal ointment which have no antibacterial activity among patients found to be colonized with MRSA in the prevention of future colonization with MRSA. As a secondary part of this objective, we will examine the impact of decolonization procedures on both infections with MRSA and soft tissue infections. In addition, as a sub-analysis to the primary objective, we will evaluate the impact of decolonization among unique randomizations (persons with first time MRSA colonization and randomization during the study).

3.2 Secondary Objectives

- a. To determine the prevalence and incidence of MRSA colonization of the nares, throat, perirectal, axilla, and groin areas among HIV infected patients and to study changes in the colonization rates over time.
- b. To determine the predictors of MRSA colonization and infection among HIV-infected persons including examination of demographics, sexual activity, hygienic practices, drug use, antibiotic and antiretroviral medications, sexually transmitted diseases, and HIV control.
- c. To evaluate the change in CD4 counts and HIV viral loads during the time of a MRSA or soft tissue infection.
- d. To characterize the molecular characteristics and the antimicrobial sensitivities of MRSA isolates in this population.
- e. To continue the previous retrospective study of MRSA infections among HIV-infected persons to examine the incidence of and describe the clinical features of MRSA infections and their response to treatment among HIV-infected patients seen within the HIV clinic at NMCSD. This study also will continue to compare those with and without MRSA infections in terms of demographic data, HIV viral loads, CD4 counts, and use of medications including antiretroviral and antimicrobial agents.

IV. BACKGROUND AND SIGNIFICANCE

MRSA was first recognized in 1961 and subsequently became a frequent cause of infections within the hospital setting. The first community-acquired MRSA infections occurred in the early 1980s. Within the past several years, the number of community-acquired MRSA cases has dramatically increased with incidence rates of 18 to 26 cases per

100,000 persons [1, 2]. In addition to individual cases, numerous outbreaks have occurred among prison inmates, athletes, military trainees, and men who have sex with men (MSM) [14-18].

Patients presenting with community-acquired MRSA infections typically present with skin or soft tissue infections such as folliculitis, furuncles, carbuncles, abscesses, or cellulitis [1, 7]. Despite that most of these infections occur in young, otherwise healthy individuals, community-acquired MRSA infections have led to a high hospitalization rate with up to 25% requiring admission for the management of the MRSA infection [1].

Severe, life-threatening cases have been described involving community-acquired MRSA infections including cases of necrotizing fasciitis; although there were no deaths in this series, significant morbidity was noted [3]. Cases of community-acquired MRSA soft tissue infections complicated by endocarditis and septic pulmonary emboli have also been reported, as well as by pyomyositis and toxic shock-like syndrome [4-6]. Several cases of necrotizing pneumonia have also been reported, especially among children [19].

The reasons that community-acquired MRSA strains cause severe infections remain unclear. Type IV *SCCmec* type, Panton-Valentine leukocidin (PVL)-positive isolates are characteristic of community-acquired MRSA. The presence of the PVL genes, which encode for a cytotoxin associated with polymorphonuclear leukocyte lysis and tissue necrosis, has been linked to cases of community-acquired MRSA soft tissue infections and pneumonia [19-21]. The most common clone of community acquired MRSA is USA 300, and this itself is likely a more virulent strain [22]. In addition, a study by Voyich and associates demonstrated that community-acquired MRSA isolates were more resistant to killing by neutrophils and caused greater host cell lysis than nosocomial strains in mouse models. This group is also examining a variety of genes that may help community-acquired MRSA strains avoid destruction by neutrophils [23]. Finally, studies have suggested that community-acquired MRSA may exhibit faster doubling times than nosocomial strains [24].

The most common risk factors for community-acquired MRSA infections among the general population are prior antibiotic use, prior hospitalization, underlying medical conditions including HIV infection, injection drug use, and contact with a person with MRSA-infection or colonization; similar risk factors are cited for those colonized with MRSA [7-10]. A study among military personnel, who resided in close proximity to one another, found that risk factors for MRSA were having a roommate with history of a soft tissue infection and having a family member or friend who worked in the healthcare setting [10]. A study among football players found that team members with frequent skin abrasions, such as linemen, were at highest risk of infection [18]. Finally, population-based studies have shown that young age and racial minorities may have a heightened risk [1, 20].

HIV infection is a known risk factor for both MRSA colonization and infection [7, 8, 11]. A recent study showed that community-acquired MRSA increased six-fold among HIV-infected persons during the years 2000 to 2003 [7]. Risk factors for community-acquired MRSA among HIV-infected patients cited in the literature include a history of MSM or intravenous drug use as the patient's HIV transmission risk factor, a low current CD4 count, high HIV viral load, and the absence of trimethoprim-sulfamethoxazole (TMP/SMX) prophylaxis [7]. Other studies found an association with exposure to public hot tubs/saunas, having a sex partner with a skin infection, and prior beta-lactam

antibiotics [13, 25]. Colonization with MRSA among HIV infected persons has been linked to low CD4 count (<100 cells/mm³), lack of TMP/SMX prophylaxis, recent antibiotic use, and hospitalizations [26, 27].

A retrospective case-control study was performed including the years of 1993-2005 among 425 HIV patients seen at the Naval Medical Center San Diego (NMCSD), of whom, 25 (5.9%) patients were found to be infected with community-acquired MRSA. All cases occurred after 2002, with a 17-fold increase from 2003 to 2005 (Chi-square test of trend 15.7, p<0.001). The annual incidence during the year 2005 among our HIV patients was 40 cases/1000 person-years compared to 2.28 cases/1000 person-years (or 741 cases/325,000) among HIV-negative persons (18-fold higher rate). In the univariate analyses, lower current CD4 count, CDC stage C vs. A, history of syphilis, and exposure to beta-lactam antibiotics in the past year were predictive of MRSA. In the multivariate model, history of syphilis and exposure to beta-lactam antibiotics remained as significant predictors [12].

Most MRSA infections among HIV-infected patients involve the soft-tissues and present as folliculitis, furuncles, carbuncles, abscesses, cellulitis, or necrotizing fasciitis [7]. HIV-infected persons presenting with a history of a “bug bite” or soft tissue infection should be evaluated for MRSA. Treatment of MRSA infections has not been standardized and the optimal therapeutic regimen remains unknown. Of note, antibiotic resistance for community-acquired strains is typically less than for nosocomial isolates due to reduced antibiotic pressures and due to the smaller chromosomal cassette. However, increasing resistance to antibiotics has been noted among community-acquired isolates, including rising rates of clindamycin resistance [28, 29].

Whether HIV patients should be screened routinely for MRSA carriage and whether decolonization procedures, with hexachlorophene (pHisoHex®) soaps and nasal mupirocin (Bactroban®), should be instituted remains unknown as there are no formal guidelines addressing these questions. Regarding screening for MRSA carriage, studies among HIV patients have suggested that high risk sexual activities and potentially perirectal carriage of MRSA may be important in the epidemiology of CA-MRSA infections. Although, a recent study showed limited use of perianal cultures for MRSA screening, this study was solely among patients at a rehabilitation unit [30a], rather than HIV patients who likely have divergent risk factors and routes of MRSA transmission. A recently presented abstract in HIV patients showed a poor correlation between MRSA nares carriage and MRSA infection [30b], hence we will evaluate the possible additive benefit of perianal and throat cultures in this cohort. Our study will examine nares, throat, axilla, groin, and perirectal surveillance cultures for MRSA among HIV patients.

Although there are no formal recommendations for the use of TMP/SMX to prevent MRSA infections among HIV-infected patients, those patients requiring this antibiotic for other indications (e.g., *Pneumocystis carinii* pneumonia or *Toxoplasma* prophylaxis) have lower rates of MRSA infection. Given the higher rates of community-acquired MRSA among HIV-infected patients and that this group may have a propensity towards recurrent infections [5], formulating preventive strategies would be useful.

The use of mupirocin nasal ointment (also known as Bactroban®) and hexachlorophene (pHisoHex®) soaps has been studied both during MRSA outbreaks and to decrease colonization and infection rates in the healthcare setting with favorable results [31-37]. The medications have a low rate of side effects and good efficacy [38, 39].

Although reported in the literature, the risk for inducing resistance to mupirocin by its use for MRSA decolonization is low even in a study applying the medication for seven consecutive years [35, 40].

We propose to prospectively study the prevalence and incidence over a two year period of MRSA colonization and infection among HIV-infected military beneficiaries, to determine predictors among this population for the development of MRSA colonization and infection and to investigate the utility of decolonization procedures in this group. In addition, we will evaluate the molecular characteristics and the antimicrobial sensitivities of isolates in this population.

We also propose to continue collecting retrospective data among HIV-infected patients at NMCSD, which has low risk and does not involve patient contact or further testing. The importance of this work is that more data regarding the risk factors of MRSA infections in this population may be useful for developing future preventive strategies. This is an ongoing study (previously IDCRP-049) that has been following HIV patients at this site since January 24, 2006 [45, 46]. Data collected on HIV patients will be retrospectively captured since 1993 or the date of the first HIV positive test, whichever is later. We will continue to evaluate the patients for MRSA events until March 1, 2011. Only existing data will be used for this study; no information collected after March 1, 2011 will be used for the retrospective study.

V. RESEARCH DESIGN

5.1 General Approach

This is a prospective, randomized, double-blind study examining the incidence and risk factors for MRSA colonization and infection among HIV-infected persons and the efficacy of decolonization procedures of mupirocin (Bactroban®) nasal ointment and hexachlorophene (pHisoHex®) soaps compared to a placebo nasal ointment and body soap. Inclusion criteria include adult (≥ 18 years) HIV-positive patients; exclusion criteria include the presence of a known allergy to mupirocin (Bactroban®) nasal ointment or hexachlorophene (pHisoHex®) soaps, pregnant or breastfeeding females, age < 18 years, persons who are healthcare providers with direct patient contact, and inability to participate in study for its two year duration. A history of MRSA infection or colonization is not an exclusion criterion for this study. Patients will be offered enrollment into the study at the time of presentation to the HIV clinic for routine care by their primary care physician and/or a study investigator. General Institutional Review Board (IRB) approved advertisement posters about the study will be posted in each clinic.

After signing the informed consent which includes a HIPAA form, the patient will be registered with the Data Coordination Center (DCC) and receive a participant identification number (PIN). A patient will be assigned a PIN centrally once the patient agrees to participate in a Infectious Disease Clinical Research Program (IDCRP) study. If a patient agrees to participate in other IDCRP studies, this same PIN will be used to link that patient to these other studies. The patient will also be assigned a subject identification number unique to the patient and this study.

Patients will then undergo swabs for determining colonization of MRSA and will fill out a questionnaire containing data regarding demographics, sexual activities,

substance use, medication use, history of soft tissue infections, and potential risk factors for MRSA. Study coordinators will review the patient's medical record for data regarding medical history. Patients will have repeated swabs, questionnaires, and review of their medical records every six months (+/- 2 months) during the two year study enrollment.

The trial will be a randomized, double-blinded study. Patients found to have a positive culture for MRSA colonization will be randomized in a 1:1 fashion to mupirocin (Bactroban®) nasal ointment plus hexachlorophene (pHisoHex®) soap for seven days or to a placebo nasal ointment (white petroleum) and a placebo body soap with no antimicrobial activity for seven days; since there is no standard therapy recommended in the guidelines for MRSA management for MRSA colonization, patients in the latter arm will receive placebos with no specific antimicrobial activity. In this design, we will ascertain if treatment for MRSA decolonization of this patient population is warranted or not. After completion of these topical medications, patients will complete a questionnaire to ascertain their adherence to these medications. Patients found to be colonized with MRSA and who reside locally (within driving distance) to the medical treatment facility will have repeat swabs (five swabs from sites listed above every four weeks (+/- 7 days) after any positive colonization cultures over the subsequent six month time period. These cultures will assist in determining if the decolonization medications were successful at eradicating the carriage of MRSA. Patients will receive one treatment course of either mupirocin (Bactroban®) nasal ointment plus hexachlorophene (pHisoHex®) soap for seven days or a placebo nasal ointment (white petroleum) and a placebo body soap with no antimicrobial activity for seven days. Patients who are initially found to be negative for MRSA on screening swabs will be re-evaluated in six months (+/- 2 months).

Patients who develop a soft tissue infection or any infection thought to be secondary to MRSA will be evaluated in the HIV clinic and will undergo wound cultures and repeated screening for MRSA colonization. CD4 counts and an HIV viral load will be obtained at the time of infection. Patient questionnaires and source documents will be completed for patients experiencing a soft tissue infection or MRSA infection.

Cultures (from colonization sampling and wound cultures) which are positive for MRSA or MSSA at the local medical treatment facilities laboratories will be sent to the San Antonio Military Medical Center (SAMMC) laboratory for confirmation of MRSA, antibiotic susceptibility testing, and molecular analysis.

We also propose to continue to review the charts (IDCRP-049) of all HIV-infected patients within the HIV clinic at NMCSD. We will review all patients' demographics, CDC stage, current CD4 counts, CD4 nadir, current HIV viral loads and medication use including antiretroviral and antimicrobial medications. We will also identify those patients who were diagnosed with MRSA infection during the time they were infected with HIV. Patients charts in the HIV clinic will be reviewed from 1 January 1993 (the beginning of CHCS) or the date of HIV positivity (whichever is later) through 1 March 2011 in an ongoing fashion. Among patients with MRSA, the following data will be collected from the charts and from CHCS: age, sex, race, years of HIV infection, CDC stage, CD4 count nadir, CD4 current value, current HIV viral load, medication use including antiretroviral and antimicrobial medications, antibiotics for MRSA, time of MRSA infection, type of MRSA infection, CD4 and viral load counts around the time of MRSA diagnosis, type of treatment, whether or not they were hospitalized and for how long, duration of the MRSA infection, any MRSA relapses, risk factors for MRSA, HSV2 serology, RPR serology,

GC/Chlamydia testing, and any antibiotics used during the previous two years. Data will be entered into a Microsoft Excel file without personal identifiers for analyses. Datasets from the prospective RV210 study and this retrospective study will be maintained in separate databases since study populations will be diverse, however linkage between datasets will be possible through linking identifiers.

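### Retrospective objective (e) has no index date or common exposure window: infection-time CD4, viral load and a two-year antibiotic look-back are listed for MRSA patients only

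*Combined protocol and SAP*

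**What the plan says.** Section 5.1 (General Approach) sets two field lists for the NMCSD chart review.

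- **All patients:** "We will review all patients' demographics, CDC stage, current CD4 counts, CD4 nadir, current HIV viral loads and medication use including antiretroviral and antimicrobial medications". No date is attached to 'current', and no look-back to medication use.
- **MRSA patients:** a longer list, introduced by "Among patients with MRSA, the following data will be collected from the charts and from CHCS". It repeats the shared fields ("CD4 current value, current HIV viral load, medication use including antiretroviral and antimicrobial medications, antibiotics for MRSA, time of MRSA infection") and adds "CD4 and viral load counts around the time of MRSA diagnosis" and "any antibiotics used during the previous two years". It also adds risk factors for MRSA and HSV2, RPR and GC/Chlamydia results.

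The review period is common to all: "Patients charts in the HIV clinic will be reviewed from 1 January 1993 (the beginning of CHCS) or the date of HIV positivity". The later of those two dates is the start, and 1 March 2011 is the end.

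Section 3.2(e) then states the aim for the two groups: "compare those with and without MRSA infections in terms of demographic data, HIV viral loads, CD4 counts, and use of medications". The drugs it names are antiretrovirals and antimicrobials. Section VII tests these differences with rank-sum and Fisher's exact tests and fits a backward stepwise logistic model for predictors of MRSA. No section defines 'current', gives patients without MRSA a reference date, or says which CD4 value or antibiotic window enters the analysis.

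**The concern.** A predictor has to be measured before the outcome, and in the same way in those who had it and those who did not. CD4, nadir, viral load and treatment all move with the course of HIV and with therapy. The plan accepts that CD4 and viral load may change with the infection itself: objective (c) compares values before, during and after a MRSA infection. Objective (e) makes no such distinction.

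Two errors become possible. A difference may appear where there is no association, or a real effect of low CD4 may vanish because CD4 had recovered by the time it was recorded. Section IV says more data on risk factors may help in developing preventive strategies. That use needs exposures that precede infection. Modelling person-time would not help by itself, because it would still be fed post-infection or mismatched exposures.

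**Working it through.** The plan states no sample size or power for this comparison, so there is no figure to reproduce. The check is to follow each analysis that the field lists allow.

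**Route 1: the shared fields in both groups.** The MRSA patient's 'current' value may fall after the infection. Section IV says all cases in the site's 1993–2005 case-control study occurred after 2002, and the review closes on 1 March 2011. If 'current' means the last value in the review, the largest gap is from early 2003 to March 2011, about 8 years. Antimicrobial use without a window can also include drugs given to treat the MRSA infection.

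**Route 2: the MRSA-only fields against the comparators' fields.** Infection-time CD4 is set against a value with no stated date, and a two-year antibiotic history against an unstated window.

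**Size for antibiotics, with no true association.** Assume a share p of patients receives a course in any year, the same in both groups and independent between years. Capture over w years is 1 − (1 − p)^w. The values of p and the comparator windows are assumptions; only the two years comes from the plan.

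- Two years: p = 0.10 gives 1 − 0.9² = 0.19; p = 0.30 gives 1 − 0.7² = 0.51.
- Against one year: (0.19/0.81)/(0.10/0.90) = 2.11; (0.51/0.49)/(0.30/0.70) = 2.43.
- Against five years: 1 − 0.9⁵ = 0.410 and 1 − 0.7⁵ = 0.832, so (0.19/0.81)/(0.410/0.590) = 0.34 and (0.51/0.49)/(0.832/0.168) = 0.21.

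**False-positive rate.** Take the group sizes of the 1993–2005 study (25 with MRSA, 425 − 25 = 400 without), capture 1 − exp(−rate × w), and assumed rates of 0.2, 0.4 and 0.8 courses a year. The chance that a two-sided Fisher test gives p < 0.05 comes from exact binomial enumeration, with two years always used for MRSA patients.

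| Comparator window | Odds ratio at 0.2 / 0.4 / 0.8 | Chance of p < 0.05 |
|---|---|---|
| 3 months | 9.6 / 11.7 / 17.9 | 0.97 / 1.00 / 1.00 |
| 1 year | 2.2 / 2.5 / 3.2 | 0.40 / 0.56 / 0.68 |
| 2 years | 1.0 / 1.0 / 1.0 | 0.04 / 0.04 / 0.04 |
| 5 years | 0.29 / 0.19 / 0.07 | 0.82 / 0.94 / 0.91 |

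**CD4.** With the same group sizes, normal values and an assumed SD of 250, the rank-sum test was simulated 4,000 times for each shift due to timing alone. Shifts of 0, 50, 100 and 150 cells give rejection in about 5%, 16%, 48% and 80% of runs.

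**The case against.** Section 5.1 describes what is collected, not what is compared. Current CD4, nadir, current viral load and medication use are recorded in both groups, so a like-for-like comparison of fields is available. The MRSA-only items sit beside treatment, hospital stay and relapse, and may serve the descriptive half of objective (e). Charts are reviewed over the same span for everyone, so dated comparator values may be obtainable. Section VII says the main retrospective results will be descriptive, and this is the last of five secondary objectives.

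Most of this stands, and it rules out several stronger readings that a reader might infer:

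- *That the analysis sets infection-time values against undated ones.* The plan does not say which values it uses.
- *That the gap is typically 8 years.* That is a ceiling. Section IV reports a 17-fold rise from 2003 to 2005, so the earliest cases were few.
- *That the antibiotic bias runs upward.* It reverses when the comparator window is longer than two years.
- *That syphilis cannot be compared because RPR is listed for MRSA patients only.* Section IV reports that in the 1993–2005 study "history of syphilis and exposure to beta-lactam antibiotics remained as significant predictors", so the charts supported that comparison before.

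The objection does not remove the problem. Using the shared fields avoids the mismatch between lists, but it leaves values that can follow the infection and drug use that can include its treatment.

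**Conclusion.** The point holds as a gap in design and specification. With no index date and no common window, neither way of carrying out objective (e) reliably shows the state before infection, and timing alone can create or hide differences in CD4, viral load and antibiotic use.

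The direction and size are unknown. The odds ratios and false-positive rates above depend on assumed antibiotic rates, comparator windows, CD4 shifts and SD, and on group sizes from an earlier study period. They show that the effect can be large in either direction, not what it will be. Only secondary objective (e) is affected; the randomized comparison of decolonization with placebo does not use these data.

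**What to change.** Amend Sections 5.1 and VII.

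- Give every patient in the comparison an index date. For MRSA patients this is the infection date. For comparators it is a date on which they were under follow-up and free of MRSA, for example matched on calendar time.
- In both groups take the last CD4 and viral load before that date, the nadir up to it, and the antiretrovirals in use on it.
- Take antibiotics and RPR or syphilis history over one identical look-back before the index date, excluding antibiotics given for the MRSA infection.
- State that only these pre-index values enter the group comparison and the model. Keep the other MRSA-only fields for describing cases.
- If comparators are sampled or matched to cases, use an analysis that respects the matching, such as conditional logistic regression.

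The cost is modest extra abstraction from charts already in scope, plus a small change to a secondary analysis. Section XV dates the current version May 2012, after the 1 March 2011 data cut-off, so some charts would have to be reopened. Full risk-set sampling is not essential: one reference-date rule for comparators, applied with the same windows, removes most of the problem.
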